## **Level of significance**

The level of significance will be taken as  $p < 0.05$  and be corrected for repeated measurements

## **10. Trial Monitoring.**

### **10.1 Clinical site monitoring.**

A monitoring plan will be arranged by the Sponsor. Monitoring will take place in accordance with York Teaching Hospitals NHS Foundation Trust's SOPs and will include, at a minimum, a Trial Initiation Monitoring Review, Trial Closure Review and regular visits to monitor CRF accuracy and completeness. An appropriate interval between monitoring visits is to be decided by the Sponsor.

## **11. Data Protection.**

### **11.1 Direct access to data.**

Authorized bodies will have direct access to all study data, including site files and source data, in order to carry out study-related monitoring, audits, ethics committee review and regulatory inspections. Anonymised waveform and annotations data will be sent to Edwards Lifesciences for the development of algorithms and the derivation of certain variables from raw data. Patients' consent for this is obtained as part of the consent process.

### **11.2 Patient data.**

Patients will be allocated a study ID number upon recruitment to the study and all personal identifiers will be removed at the earliest opportunity. Any identifiable information such as contact details or consent forms will be stored in a site file held in a locked filing cabinet. Non-identifiable data will be held on a Trust, password protected computer.

### **11.3 Confidentiality.**

Full medical confidentiality will be maintained in accordance with law in the UK and The Netherlands and the study will be conducted according to GCP guidelines. No patient's name or address will be disclosed to any third party. Patients will not be identifiable in any publication that arises as a result of this study. The study will comply with GDPR.

## **12. Ethical Considerations and Approval.**

### **12.1 Ethical considerations.**

Participants in this study will not have to undergo any additional clinical investigations above and beyond their usual care and will not have to attend any additional hospital appointments.

Full medical confidentiality will be maintained according to UK law for York Teaching Hospitals NHS Foundation and The Netherlands law for University Medical Centre Groningen and the study will be conducted according to GCP guidelines.

The study information and all data will be stored for a period of at least 5 years.

All investigators and research teams will receive training in relevant areas such as GCP, and Standard Operating Procedures (SOPs).

A monitor appointed by the York Teaching Hospitals NHS Foundation Trust will monitor the conduct of the study.

### **12.2 Ethical approval.**

Ethics approval will be sought from an appropriate ethics committee.

### **12.3 Study withdrawal.**

The right of any patient to refuse to participate in the study without giving reasons shall be respected. After the patient has entered the study, all clinicians are free to give alternative treatment to that specified in the protocol, at any stage, if he/she

feels it to be in the best interests of the patient. However, the reason for doing so shall be recorded and the patient will remain within the study for the purpose of data analysis according to the treatment option to which they have been allocated. Similarly, all patients are free to withdraw at any time from the protocol treatment and study follow-up without giving reasons and without prejudicing his/her further treatment.

## 13. Safety Reporting

All adverse event reporting will be carried out in accordance with the Sponsor's Research Related Adverse Event Reporting Procedures.

For all adverse events, the Clinical Investigator will take appropriate action to ensure the safety of all participants and staff in the study.

### 13.1 Definition of Adverse Events/Reactions

#### Adverse Event (AE)

An adverse event is defined as any untoward medical occurrence that occurs to a study participant during the course of the study. Information about adverse events will be collected from the beginning of any study related procedure. For the purpose of this study this is defined as the induction of anaesthesia

For the purpose of this study the adverse events that will be recorded are those that may occur as a result of the sensors applied. Such adverse events will include, but will not be limited to:

- Thermal burns
- Digit ischaemia or injury
- Pain at sensor sites
- Reaction whether due to allergy or otherwise to the sensors
- Any other adverse event deemed relevant by the Chief Investigator.

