## **6. Treatment of Patient Participants**

When the participant arrives in the operating room they will be connected to standard monitoring including non-invasive blood pressure, ECG and SpO2. An arterial cannula (standard care) will be placed in a radial artery (brachial artery if radial is

unable to be cannulated) under local anaesthesia and connected to a FloTrac IQ transducer and haemodynamic data will be displayed on the Hemosphere platform. This monitor will be designated monitor 1. Subsequently, all study sensors will be applied. A Foresight sensor will be placed on the flank, above the kidney (localised by ultrasound) and one on the skin above the quadriceps, at a muscle dense location. Two sensors will be applied to the forehead and will be secured with a headband if necessary. The Foresight sensors will also be connected to the Hemosphere monitor 1. A ClearSight cuff will be placed on a suitable finger on the ipsilateral hand and connected to a second Hemosphere monitor, designated monitor 2. Both monitors will be synchronised for date and time.

A period of ten minutes will be used to capture baseline data before anaesthesia is induced. All treatment will be as per standard institutional care and none of the sensors will be used to guide treatment, except for the FloTrac sensor, which will be used according to routine clinical practice.

All interventions during the procedure including but not limited to fluid therapy, vasoactive drug administration and positional changes will be entered on to the hemosphere platform (monitor 1), and at the end of surgery, all data will be downloaded from each Hemosphere monitor.

Monitor 1 will provide measurements of cardiac output, cardiac index, stroke volume variation, stroke volume, stroke volume index, hypotension probability index, pulse rate, and systolic, diastolic and mean arterial pressure from the invasive arterial waveform and cerebral, renal and muscle tissue oxygen saturations.

Monitor 2 will provide measurements of cardiac output, cardiac index, stroke volume variation, stroke volume, stroke volume index, hypotension probability index, pulse rate, and systolic, diastolic and mean arterial pressure from the non-invasive arterial waveform.

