## **8.2 Loss to follow-up.**

It is highly unlikely that there will be any loss to follow up as data collection ceases at the end of surgery.

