## **8.3 Trial closure.**

The study shall end when the last patient has been has completed surgery.

At the point of study closure the Chief Investigator shall notify the Sponsor in writing that the study has ended. This shall be done in accordance with the York Teaching Hospitals NHS Foundation Trust R and D unit SOP on Trial Closure. Study data will be archived in accordance with the York Teaching Hospitals NHS Foundation Trust and University Medical Centre Groningen SOP

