### **13.3 AE Follow-up**

Adverse events will be followed up by the research team to their conclusion. Follow up of adverse events will cease at hospital discharge or Day 10 whichever is reached first.

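### Adverse-event collection is defined to start at induction, although the study sensors are applied and recording for ten minutes before it

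*Protocol*

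**What the plan says.** **Start of collection.** Section 13.1 of the Protocol gives a principle, "Information about adverse events will be collected from the beginning of any study related procedure", and then an operational definition, "For the purpose of this study this is defined as the induction of anaesthesia". It restricts what is logged: "the adverse events that will be recorded are those that may occur as a result of the sensors applied". Its examples include burns, finger injury, pain where a sensor sits, and reactions to the sensors.

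Section 6 sets the order of events in theatre. The arterial cannula is placed under local anaesthesia as standard care. Then "Subsequently, all study sensors will be applied": two ForeSight sensors on the forehead, one on the flank, one over the quadriceps, and a ClearSight finger cuff. Then "A period of ten minutes will be used to capture baseline data before anaesthesia is induced".

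**End of collection.** Section 8.2 says that "data collection ceases at the end of surgery". Section 8.3 says "The study shall end when the last patient has been has completed surgery". Section 13.3 says "Follow up of adverse events will cease at hospital discharge or Day 10 whichever is reached first". Section 13.4 has serious events followed until they conclude, with no time limit. Section 13.1 defines an AE as something that happens while the study is running.

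**The concern.** In an observational study the sensors are the only thing added to routine care, and sensor harm is the only kind of event that section 13.1 singles out for recording. A window that opens after the sensors have been attached and switched on does not match that purpose. It also leaves out a planned period in which the patient wears the sensors and is not yet under general anaesthesia, and so can say that a cuff or sensor hurts.

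What is at stake is a complete and consistent sensor-safety record, not an efficacy or agreement result. Two sites in two countries must apply the same rule. One could log pre-induction sensor pain by relying on the first sentence of the definition, and the other could leave it out by relying on the second. Both would be following section 13.1.

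At the other end, a study that is declared over at the last operation sits awkwardly with follow-up duties that run beyond it.

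**Working it through.** No sample-size, power or error-rate figure is involved. The check sets the stated timelines side by side.

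**1. Order of events before surgery (section 6).** Arterial cannula, then four ForeSight sensors (2 + 1 + 1) and one ClearSight cuff, then ten minutes of baseline, then induction.

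**2. Is induction the first study procedure?** No. Section 6.1 leaves anaesthesia to local practice, and section 5.1 says that all patients receive standard institutional care. Induction is therefore routine care. The first study-specific sensor goes on before it. The operational definition in section 13.1 contradicts both the principle beside it and the sequence in section 6.

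**3. Exposure outside the window.** Per patient: at least 10 minutes of baseline, plus application time that the protocol does not give. Over the planned 100 patients: 100 × 10 = 1,000 patient-minutes, and 1,000 / 60 ≈ 16.7 patient-hours, as a minimum. This measures exposure. It is not a count of missed events.

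**4. Which events are lost on a literal reading?**
- Begins after induction: inside the window.
- Begins before induction and persists (a burn, a finger injury, a skin reaction): still present once the window opens, so it can be recorded.
- Begins and resolves before induction (for example, pain relieved by moving a sensor): not captured.

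Only the third group is lost. The catch-all item in section 13.1, which lets the Chief Investigator add other relevant events, widens the type of event and not the time window.

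**5. The other end.**
- Section 8.2 stops data collection at the end of surgery. Taken literally, this conflicts with section 13.3 for every patient. Read as referring to study measurements, it does not.
- Section 8.3 ends the whole study at one point, the last patient's operation. Patients whose follow-up under section 13.3 is already finished by then are unaffected. Those operated on shortly before closure still have follow-up to run.
- Because section 13.1 ties an AE to the course of the study, the status of a new event that first appears in those patients after closure is unclear.
- Section 13.4 is open-ended, so follow-up of a serious event can also outlast the stated end.

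**The case against.** The strongest reply is that little is lost in practice. Patients wake after surgery, section 3 includes the post-anaesthetic care units of both sites in the study setting, and section 13.3 provides for follow-up after surgery. Injuries that persist can be recorded then. Section 2.1 rates the sensor risk as low, section 7 describes the devices as CE marked and used as intended, and neither the outcomes in section 9.1 nor the analyses listed in section 9.4 use AE counts. Section 13 also refers AE reporting to Sponsor procedures that are not shown. On closure, section 8.3 can be read as an administrative rule: it does not cancel sections 13.3 and 13.4, which impose duties of their own.

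Most of this stands, and it limits the size of the point. It does not remove the contradiction. Section 13.1 gives a study-specific definition that disagrees with section 6, and the Sponsor's general procedures cannot be assumed to override it.

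Three stronger readings are tempting, and the documents do not support them:
- *The pre-induction period is the patient's only chance to report.* It is not, because patients can also report after emergence. It is the planned period before surgery in which they wear the sensors and are not yet anaesthetised.
- *Sensor AE counts are materially biased downwards.* Any loss is in that direction, but the protocol gives no pre-induction event rate, and only transient events drop out.
- *Closure cuts off follow-up at both sites.* There is one study-wide end. If one site finishes well before the other, its patients may have completed non-serious AE follow-up by then.

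**Conclusion.** The start of AE collection is wrong as written. It contradicts the principle stated in the same section and the procedure in section 6, and it leaves at least ten minutes of sensor exposure uncovered in each of the 100 planned patients. The practical loss is limited to sensor-related events that come and go before induction. Their number is unknown and probably small. No primary or secondary outcome is affected, nor are the sample size and listed analyses. This is a wording error worth correcting and not a threat to the study.

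The end-of-study mismatch is real but narrower. It concerns mainly patients operated on shortly before closure, and it is a matter of making sections 8.2, 8.3, 13.1, 13.3 and 13.4 agree.

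The conclusion assumes that section 6 describes the order actually followed, and that the Sponsor procedures cited in section 13 do not already set an earlier start.

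**What to change.** - **Section 13.1:** define the start of AE collection as application of the first study sensor, ForeSight or ClearSight, in place of induction.
- **Section 8.3:** define the end of the study as completion of AE follow-up in the last patient, and say how a serious event still open at that point is handled.
- **Section 8.2:** limit the statement about the end of data collection to haemodynamic and oximetry data.
- **Section 13.3:** state the event from which Day 10 is counted, since the new study end would depend on it.

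The cost is a short amendment, a few more minor AEs to record, and a slightly later closure. If Day 10 is counted from surgery, which the protocol does not say, the delay is at most ten days, apart from open serious events. Study measurements and patient care do not change.

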#### Serious Adverse Event (SAE)

An adverse event is defined as serious if it results in one of the following:

- Death
- A threat to life

- A new in-patient hospitalisation (not including planned, elective treatment)
- Prolonging of an existing hospitalisation
- Persistent or significant disability or incapacity
- A congenital anomaly or birth defect in a subsequent pregnancy (not expected in this sample of patients)

### Serious Adverse Reaction (SAR)

An SAE will be deemed to be an SAR if there is thought to be a possible, probable or definite relationship to the volume of fluid therapy, the use of vasopressors, or the omission of clinically significant treatment. Causality will be rated for all SAEs as follows:

#### *Not related*

There is clear alternative explanation for the AE or it has no reasonable temporal relationship to the volume of fluid therapy or use of vasopressors.

#### *Unlikely to be related*

The AE may be temporarily linked to volume of fluid therapy or use of vasopressors but is much more likely to be due to other causes.

#### *Possible*

The AE has a reasonable temporal relationship with volume of fluid therapy or use of vasopressors but could equally well be explained by these or other causes.

#### *Probable*

The adverse event may be due to an alternative cause but it will follow a pattern of a known response and/or a reasonable temporal relationship to volume of fluid therapy or use of vasopressors.

#### *Definitely related*

The adverse event cannot be explained by an alternative cause and either follows a pattern of a known response and/or a reasonable temporal relationship to volume of fluid therapy or use of vasopressors

### Suspected Unexpected Serious Adverse Reaction (SUSAR)

A SUSAR is an adverse event that is serious, thought to have a possible, probable, or definite relationship to volume of fluid therapy or use of vasopressors and is unexpected.

Expectedness will be rated as:

*Unexpected*

The nature and/or severity of the event is not consistent with the applicable information about volume of fluid therapy or use of vasopressors.

*Expected*

The nature and/or severity of the event is consistent with the applicable information about volume of fluid therapy or use of vasopressors.

### **13.2 Clinical Management of Adverse Events**

The supervising clinician will manage any adverse events that should occur. Advice will be provided by the Chief Investigator as necessary. Documentation of any action taken will be recorded in the medical notes and communicated to other relevant parties as necessary.

### **13.3 AE Follow-up**

Adverse events will be followed up by the research team to their conclusion. Follow up of adverse events will cease at hospital discharge or Day 10 whichever is reached first.

### **13.4 SAE/SUSAR Follow-up**

All SAEs or SUSARs will be followed up to their conclusion irrespective of the timeframe of the follow-up period. If necessary this will involve telephone interviews or, if deemed necessary and the study participant is willing, an extra out-patient visit for review by the research team. Any patient discharged home with an ongoing SAE/SUSAR shall be given 24 hour contact details for the research team.

#### **SAE NOTIFICATION**

Within 24 hours of becoming aware of anSAE, please fax a completed SAE form to the York Foundation Trust R&D Unit

on:

**[contact]**

## 14. Financial details

### York (50 patients)

Sponsor set up fees 2000 GBP  
Chief Investigator time (0.5 PA for 12 months) 6198 GBP  
Mid band 4 study co-ordinator 12 079 GBP  
Mid Band 7 research nurse 0.2 WTE for 12 months 17 300 GBP  
Monitoring 5000 GBP  
Archiving 500 GBP  
Stationary and consumable 500 GBP

**Total 43 577 GBP**

### Groningen (50 patients)

Research nurse (300 EUR/hr) – 50 patients at 2 hours per patient 30 000EUR  
Local project manager (150EUR/hr) – 35 hours 5250 EUR  
Overheads at 30% 10 575 EUR

